7.4 Qualitative Data Collection

Participants who are randomized and consented to participate in an in-depth interview will complete the interview directly after their clinic visit or within one week of the visit. Study staff will conduct all interviews. These individuals are all trained in qualitative research techniques, patient-centered counseling, and contraceptive counseling. All discussions will be conducted in a welcoming, culturally-sensitive manner.

Audio recording of all interviews will be transcribed for qualitative data analysis, and then the recordings will be destroyed.

Semi-structured interview

After the participant has completed their appointment and post-visit survey, the interviewer (a research staff member) will explain the process of the semi-structured interview. The interviewer will reiterate the confidentiality aspect and the right of the participant to ask questions or decline to answer specific questions, and ask for permission to begin recording.

Interviews will be conducted either in-person in a private space at the clinic, or over Microsoft Teams or Zoom, both HIPAA compliant video conferencing programs. Microsoft Teams and Zoom interviews can take place either at the clinic, or remotely at the participant's home or another private space outside of the clinic.

The interview consists of a series of open-ended questions about their experience using the decision support tool, HIV risk perception, screening and counseling about HIV prevention and PrEP, as well as perceived effects on the subsequent decision-making process about PrEP use and thoughts and perceptions about patient-provider communication about the social determinants of health and structural trauma/vulnerability. The interviewer will maintain a neutral and patient-centered tone and will ask probe questions to prompt more exploration of relevant topics.

Once the participant agrees to be audio-recorded, the interviewer will switch on the HIPAA compliant digital recorder and begin the interview. Interviews over Microsoft Teams or Zoom will be automatically recorded using a HIPAA compliant system. The interviewer will remind the participant that the interview is being recorded at the beginning of the conversation. The audio recording will automatically be saved to the interviewer's desktop and the interviewer will immediately save the audio recording to a secure server and delete the audio recording from their desktop after it has been saved to the server.

Below are procedures for each type of interview:

- In-person interview:
 - Directly after appointment - If the qualitative researcher conducting the interviews is available and at the clinic that day, the participant will be offered an in person interview to take place directly after their appointment.
 - Within one week of appointment- If the qualitative researcher conducting the interviews is available to meet in person at the clinic

within one week of the appointment, the participant will be offered an opportunity to come back to the clinic to participate in an in person interview. The RA will schedule a time for the participant to come back to the clinic and will follow up over with the participant by phone to confirm the appointment.

- Video interview using Microsoft Teams or Zoom at the clinic
 - Directly after appointment – If the qualitative interviewer is available, the participant will be offered an opportunity to have a video interview directly after their appointment. The RA will accompany the participant to a private room in the clinic where the interview will take place. The RA will help with setting up the interview and will be there to give the participant a gift certificate once the interview is finished.
 - Within one week of appointment – The participant will also be offered the opportunity to return to the clinic within one week of their appointment to participate in a video interview. The RA will schedule a time for the participant to come back to clinic and will follow up over with the participant by phone to confirm the appointment.
- Video interview using Microsoft Teams or Zoom at home
 - Participants with internet at home, private servers, and computers or tablets with video cameras, can choose to participate in a video interview at home within one week of their appointment. Participants will be asked to have the interview in a private, quiet, and confidential space where they feel comfortable. The RA will schedule a time for the interview to take place. The RA will mail the participant a gift certificate after the interview has taken place.

8. DATA ENTRY

8.1 Entering Data

Survey data for each participant will be entered into REDCap in real-time, either in-person or over the phone.

Qualitative data attained from audio transcriptions will be imported into NVivo 10 software, or an alternative qualitative data analysis software package, for analysis.

8.2 Checking Data

Downloaded de-identified survey data will be exported to Excel and then to STATA for analysis. Tabs will be run in Stata to identify any errors in survey data. This will include the examination of descriptive statistics for plausibility (i.e. participant ages), distribution, and missing values.

8.3 Data Cleaning

Quantitative data

Quantitative data required for primary analyses will be cleaned and locked before primary analysis begins. The raw data will be saved in a separate directory to ensure that it will not be manipulated, saved over, or deleted (i.e. c:\data\raw_data). Any manipulated datasets, including cleaned data, will be saved with a new name in a separate directory (i.e. c:\data\cleaned).

Research staff will document any changes performed during the data cleaning process through comments or notes in the do-file. The goal is that a future team member who opens the do-file will be able to understand exactly what was done to the data and the purpose of each change. Comments will be inserted using an asterisk before text.

A codebook for quantitative data will be created, maintained, and updated throughout the data cleaning process. Any new variables, including dummy variables, will be documented with its type (string or numeric) and a description in plain language.

Missing values in the raw data set will be indicated by a variation of “888” or “999.” These missing values will be recoded with either a period (“.”) for missing numeric variables or a blank space (“ ”) for character values. If a correction is verifiable through review of an individual’s record, it will be replaced with the correct value in the dataset and documented within the do-file. Any inconsistencies in data entry (i.e. Male, male, M, mael) will be cleaned using the *replace* or *generate* command.

Qualitative data

Qualitative data, captured through transcribed interview audio recordings, will be closely monitored for quality. A research staff member will examine transcriptions for sections the transcription service had identified as “unintelligible” (due to background noise, low audio quality). The staff member will listen to these audio recordings again to ensure all accessible data was captured. Any changes will be reviewed by another staff member.

9. DATA MANAGEMENT

Only personnel approved through the IRB will have access to study data. As much data as possible will be collected and stored electronically in order to minimize the number of pieces of paper containing PHI and the possibility for participant data to be lost or breached. Collecting data electronically also eliminates the possibility for study staff to make errors in data entry when transferring data from paper to electronic storage.

All paper files are kept in a locked file cabinets that are accessible only to the PI, Co-PI and study staff. Additionally, electronic files such as the interview recordings are kept on a secure server or encrypted laptop belonging to the PI or study staff and accessible only with passwords.

9.1 Data storage

9.1.1 Consent forms

Consent forms will be administered electronically (e.g. through Qualtrics or REDCap) using iPads. Paper consent forms will be used as back-up in the event of technological difficulties. Paper consent forms will be stored in locked file cabinets in a locked office for three years after study completion.

9.1.2 Surveys

All patient surveys will be administered via REDCap using secure iPads. Paper surveys will only be used as back-up in the event of technological difficulties, and will be locked in HIPAA-compliant bags and entered into REDCap as soon as possible. Paper surveys will then be destroyed (i.e. shredded and disposed of at FDOH).

Survey data will then live in the secure UCSF REDCap database, to which UCSF and FDOH staff will have access. All user actions in REDCap are tracked by user and time (for example, editing or downloading data). Participant names and contact information will be marked as PHI and will not be downloadable. Only de-identified survey data will be able to be downloaded.

9.1.3 Contact information

Contact information will be entered directly into REDCap. Paper contact information will only be used as a back-up if technological issues occur in clinic. Paper contact information will be locked in HIPAA-compliant bags and entered into REDCap as soon as possible. Paper contact information will then be destroyed.

All contact information will be deleted 1 year after the last participant is contacted at her 3 month follow-up.

9.1.4 Audio recordings

All audio recordings of intervention sessions will be managed in accordance with [name] standard operating procedures. This includes promptly transferring recordings off of the recording device and onto a secure server. All audio recording transfers to UCSF will occur by secure, encrypted file transfer using MoveIt (approved by FDOH).

9.2 Data transfer

All hard copies of PHI will be transferred directly in the care of a research staff member from their sites in a HIPAA approved bag to the main research office at FDOH, where they will be stored in a secure location.

Electronic data, namely audio files, will be transferred from audio recorders to a secure server as soon as possible and before more than 3 files are on any one recorder. Once transferred, audio files are immediately deleted from recorders. While being transported, recorders should be brought directly to the main research office and not be left in cars or any other possibly

vulnerable location. All audio recorders will require a passcode to unlock. (These protocols were formed based on security consultations from past studies with this PI involving audio recordings).

We will use MoveIt encryption software for all internet file transfers from FDOH to UCSF, and to non-UCSF addresses, including transcription services, which is Home Row Transcription Services for this study. For all file transfers, we will ensure that all passwords follow UCSF guidelines, including being a minimum of 7 characters and containing three of the four categories of characters (lower-case letters, upper-case letters, numbers, and symbols). We will ensure that all files are encrypted and securely transferred using MoveIt. We will communicate all passwords related to file transfers over the phone.

9.3 Security of files in use

All work will be done either directly on secure server or on an encrypted, institution-approved laptop in a private and secure setting.

10. DATA ANALYSIS

Community advisory board members will be involved in an iterative manner in all stages of planning of analyses and in data interpretation.

10.1 Methods of Quantitative Data Analysis

See Statistical Analysis Plan.

## LIST OF ABBREVIATIONS

Abbreviations	Definitions
AE	Adverse Events
DCS	Decisional Conflict Scale
DST	Decisional Support Tool
EMR	Electronic medical record
HIV	Human Immunodeficiency Virus
ITT	Intention-to-treat
MRN	Medical record number
PP	Per protocol
PrEP	Pre-exposure prophylaxis

## 1. Study overview

To address the significant barriers to PrEP implementation for those who were assigned female at birth and self-identify as a woman and address racial inequities in HIV prevention in the United States (US), a novel approach that accounts for multilevel influences is necessary. This study is one part of a multi-component project and involves a patient-level intervention in one public health family planning clinic in Duval County Florida, where the majority of patients are women of color. The area has one of the highest HIV incidence rates among women in the US. The investigators developed a tablet-based decision support tool that helps users learn about HIV vulnerabilities and HIV prevention strategies to inform how they consider options for reducing their likelihood of acquiring HIV. Participants will be randomized to use the HIV decision support tool before their visit or standard counseling (without the use of the tool) and will be surveyed about the use of the tool, experiences with HIV prevention counseling, and intentions about the use of HIV prevention. A subset of participants, all individuals who self-identify as a woman and as Black or Latina, will also complete a post-clinic visit interview. The investigators will follow-up with participants at three months following their initial visit to see if they have initiated the HIV prevention method(s) they chose at their visit. The main outcomes will include a quantitative and qualitative assessment of PrEP or other HIV prevention use, decisional certainty, and satisfaction with information about HIV prevention options.

### 1.1 Study objectives

Aim 1a: Women who use the HIV prevention decision support tool will be more likely to have initiated PrEP within 3 months compared to women who received standard counseling at the time of their initial appointment.

Aim 1b: The HIV prevention decision support tool will increase women's knowledge of PrEP and other HIV prevention methods compared to women who received standard counseling at the time of their initial appointment.

Aim 1c: The HIV prevention decision support tool will increase participants' decisional certainty in their choice of an HIV prevention method compared to women who received standard counseling at the time of their initial appointment.

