7.3 Quantitative Data Collection

Data from surveys will be entered into REDCap by participants with the use of a tablet computer, and by research staff in real-time over the phone during follow-up.

After obtaining informed consent, research staff will explain and administer the pre-visit survey, which collects information on HIV prevention knowledge and interest, before the intervention participants use the decision support tool.

After the participant's visit with the provider, they will be asked to complete a post-visit survey about their clinic visit and counseling, risk perception, decision making, sexual history, and their experience with the decision support tool if they are in the intervention arm.

Three months post-visit, research staff will follow-up with participants by phone to administer a short survey and ask participants about their chosen HIV prevention method, and if they initiated PrEP.

Upon completion of the study, research staff will extract data from the medical record pertaining to participants' PrEP prescriptions, history of sexually transmitted infections, zip code, and insurance status.

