##### 2.1.2.2 Secondary variables

- **Number of Patients Reporting PrEP use:** Participants will be contacted at follow-up and asked if took PrEP in the past 3 months regardless of where it was obtained.

- **Patient-Perceived HIV risk:** Participants will be asked about how worried they are about getting HIV in the next 6 months.
- **Knowledge of PrEP:** Participants will be asked a series of questions about PrEP to assess PrEP knowledge.
- **Decisional Conflict:** Participants will be asked questions derived from the Decisional Conflict Scale to provide a measure of decision quality about their HIV prevention decision immediately following their visit.
- **Interpersonal Quality of HIV Prevention Care:** A scale for patient-centered HIV prevention counseling focusing on patient preferences and reflecting satisfaction and confidence in the counseling session, derived from the Interpersonal Quality of Family Planning Care Scale developed by the PI.
- **Intention to Use Any HIV Prevention Method:** Participants will be asked if they plan to use any HIV prevention method after the initial visit.
- **Satisfaction with Information Received about HIV Prevention:** Participants will be asked about their satisfaction with HIV prevention counseling.
- Confidence in decision to use an HIV prevention method. A one-time, one-item measure of certainty of plan to use HIV prevention after the initial visit. Participants can select from 4 options: 1 ("completely unsure"), 2 ("mostly unsure"), 3 ("mostly sure, but not 100%"), or 4 ("100% sure").
- **Perceived Quality of Information Received about HIV Prevention:** Participants will also be asked questions about the perceived quality of the HIV prevention information they received during their health care visit.
- **Acceptability of HIV Prevention Methods:** Participants will be asked to rate their preference for a method (even if they never used it). Participants can select from condoms, PrEP, PEP, treatment as prevention, regular partner testing, or other method.
- **Acceptability of the Decision Support Tool:** Participants in the experimental arm are asked four questions about their experiences using the DST.
- Perception of the Decision Support Tool: Participants in the experimental arm will be asked about the degree to which they liked/disliked the tool. Response options vary: "I did not like it at all", "I somewhat disliked it", "I somewhat liked it", "I really liked it".

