## 2.2 Hypotheses

1. The intervention will result in significantly higher number of PrEP prescriptions compared to the control group.
2. The intervention will result in significantly higher number of individuals reporting PrEP initiation compared to the control group.
3. The intervention will result in significantly higher level of patient-perceived HIV risk post-visit compared to the control group.
4. The intervention group will report significantly higher PrEP knowledge compared to the control group.
5. The intervention group will report significantly higher quality of HIV care compared to the control group.
6. The intervention group will report significantly higher intention to initiate any HIV prevention method compared to the control group.
7. The intervention group will report significantly higher satisfaction with information received about HIV prevention compared to the control group.
8. The intervention group will report significantly higher confidence in decision to use an HIV prevention method compared to the control group.
9. The intervention group will report significantly higher acceptability of HIV prevention methods compared to the control group.
10. The intervention group will report significantly lower decisional conflict, as documented by the full scale and subscales, compared to the control group.
11. The intervention will result in significantly higher number of individuals reporting ongoing PrEP use at 3 months post-visit compared to the control group.
12. A significantly higher proportion of the intervention group will report use of any HIV prevention method at 3 months-post study initiation compared to the control group.
13. A significantly higher proportion of the intervention group will report significantly higher continuation of any HIV prevention method at 3 months-post study initiation compared to the control group.
14. The intervention group will report high acceptability of the DST.
15. A high proportion of the intervention group will report positive impression of the DST.
16. A high proportion of the intervention group will report willingness to use the DST at a future visit.
17. A high proportion of the intervention group will report willingness to recommend to a friend.
18. The intervention group will report high satisfaction with the DST.

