#### 3.3.2 Secondary data analyses

The analysis plan for H2-H9 is as follows:

Summary statistics will be presented by treatment group. Differences between study groups at  $t_1$  will be assessed through  $\chi^2$  or Fisher's exact tests as appropriate. Cohen's d will be calculated as measure for effect size.

The analysis plan for H10 is as follows:

Full scale and subscales will be scored as instructed in the [Decisional Conflict Scale](#) manual. Summary statistics will be presented by treatment group for the full scale and by subscale. To assess differences in scale score distribution between groups, we will perform t-tests or sign tests as appropriate. In case of high positive skew (as common in the literature) we will create binary variables demarcating no conflict versus any conflict and perform  $\chi^2$  tests. Cohen's d will be calculated as measure for effect size.

The analysis plan for H11-H13 is as follows:

Summary statistics will be presented by treatment group. Differences between study groups at  $t_2$  will be assessed through  $\chi^2$  or Fisher's exact tests as appropriate. Cohen's d will be calculated as measure for effect size.

The analysis plan for H14-H18 is as follows:

Summary statistics will be presented for the intervention group.

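### Aim 1b covers knowledge of PrEP and of other prevention options, but only PrEP knowledge is tested, and without using the knowledge recorded before the tool

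*SAP*

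**What the plan says.** **The aim.** SAP 1.1, Aim 1b: "The HIV prevention decision support tool will increase women's knowledge of PrEP and other HIV prevention methods". The comparison is with standard counselling, at the initial appointment.

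**The outcome.** SAP 2.1.2.2 defines a single knowledge outcome: "Participants will be asked a series of questions about PrEP to assess PrEP knowledge". Protocol 7.1.2 defines it in the same way.

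**The hypothesis.** H4 in SAP 2.2: "The intervention group will report significantly higher PrEP knowledge compared to the control group". No other hypothesis from H1 to H18 concerns knowledge.

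**The analysis.** H4 belongs to the SAP 3.3.2 block headed "The analysis plan for H2-H9 is as follows". That block reads "Summary statistics will be presented by treatment group. Differences between study groups at" t1, and the test is chi-square or Fisher's exact. No covariate is named. The t2 block ("The analysis plan for H11-H13 is as follows") contains no knowledge hypothesis.

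**The pre-visit measure.** Protocol 7.3 has staff "administer the pre-visit survey, which collects information on HIV prevention knowledge and interest, before the intervention participants use the decision support tool". Protocol 3.2.3 places this survey before randomisation.

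**The concern.** There are two separate problems.

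First, the aim is wider than anything that will be tested. The tool covers several prevention methods (Protocol 1.1), so knowledge of the others is a substantive part of what it might change. As planned, a significant H4 could be reported as meeting Aim 1b although knowledge of condoms, PEP, treatment as prevention or testing was never compared between arms.

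Second, women probably arrive with very different knowledge, and that is likely to explain part of the variation in what they know afterwards. The trial records something about this for every participant before allocation, yet the effect analysis for H4 does not use it. The cost is a less precise estimate than the same data could give.

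**Working it through.** **1. Aim against endpoints**

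| Item | PrEP knowledge | Knowledge of other methods |
|---|---|---|
| Aim 1b (SAP 1.1) | yes | yes |
| Outcome (SAP 2.1.2.2, Protocol 7.1.2) | yes | none |
| Hypothesis (SAP 2.2) | H4 | none |
| Test (SAP 3.3.2) | chi-square or Fisher at t1 | none |

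The nearest outcomes do not fill the right-hand column. Acceptability of methods is a preference rating. Satisfaction with the information and its perceived quality are opinions about the counselling. This part of the point needs no assumption.

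**2. Where pre-visit knowledge could enter**

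- SAP 2.1.1 lists demographic and behavioural baseline variables; knowledge is not among them.
- SAP 3.1 plans tests of baseline differences in measured variables, which could include it.
- SAP 3.3.2 uses no baseline value in the H4 comparison.

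It may therefore appear in a balance table, but it plays no part in the effect estimate.

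**3. The plan's own power figure**

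The only one (SAP 1.5, Protocol 7.2) is 320 women for PrEP uptake of 5% against 15%, with 80% power and two-sided alpha 0.05. Without continuity correction:

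n per arm = [1.96·√(2·0.10·0.90) + 0.8416·√(0.05·0.95 + 0.15·0.85)]² / 0.10² = 140.1, rounded up to 141 (282 in total).

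With the correction:

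(140.1/4)·[1 + √(1 + 4/(140.1·0.10))]² = 159.5, rounded up to 160 (320 in total).

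The stated figure is reproduced. It says nothing about knowledge; I use it below only as an illustrative number analysed.

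**4. Size of the precision loss (illustrative)**

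Assumptions not in the documents: a continuous t1 score, correlation r with the pre-visit measure, 160 analysed per arm.

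- Variance ratio, adjusted to unadjusted: 1 − r².
- Unadjusted detectable difference at 80% power: (1.96 + 0.8416)·√(2/160) = 0.313 SD.
- Adjusted detectable difference: 0.313·√(1 − r²).
- Power at a true difference of 0.313 SD: Φ(2.8016/√(1 − r²) − 1.96).
- Equivalent unadjusted sample: 320/(1 − r²).

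| r | Variance ratio | Detectable difference (SD) | Power at 0.313 SD | Equivalent N |
|---|---|---|---|---|
| 0 | 1.00 | 0.313 | 80% | 320 |
| 0.3 | 0.91 | 0.299 | 84% | 352 |
| 0.5 | 0.75 | 0.271 | 90% | 427 |
| 0.6 | 0.64 | 0.251 | 94% | 500 |

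The t1 survey normally follows the visit directly, so more than 320 may be analysed. With all 384 (192 per arm) the unadjusted detectable difference is 0.286 SD. The variance ratios do not change.

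**5. What the documents leave open about the t1 measure**

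The descriptions of the post-visit survey (Protocol 3.2.3 and 7.3, SAP 1.6) do not mention knowledge, although H4 is tested there. SAP 3.1 has a general rule for scoring scales, but nothing specific to knowledge says how a set of questions becomes the categorical variable that a chi-square test needs.

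**The case against.** The mismatch in Aim 1b is plain on the text; the objections concern the rest.

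- **Adjustment is a choice, not a requirement.** Aim 1b is a between-arm contrast, and in a 1:1 randomised trial the unadjusted test answers it without bias. Its error rate already allows for chance imbalance. This stands: a reader might infer that the H4 test is invalid, and it is not. The issue is efficiency on one secondary hypothesis, for which no power is claimed.
- **The pre-visit items may not match the t1 items.** The protocol says only that the survey "collects information on HIV prevention knowledge and interest, before the intervention participants use the decision support tool"; it does not say that the same PrEP questions are asked or scored. This limits the likely gain but does not defeat the change, because a covariate need not be the same instrument as the outcome.
- **The 1 − r² factor belongs to a linear model of a continuous score, whereas the SAP plans a categorical test.** This stands as a limit on the figures. A reader should not take 33% more participants (r = 0.5) or 56% more (r = 0.6) as what this trial loses.
- **Timing.** A reader might count testing only at t1 as a further shortfall. The documents do not support that: Aim 1b refers to the initial appointment, and t1 follows it directly.
- **Weight.** The protocol's own aim (section 1.2) does not mention knowledge, and the overreach is one phrase in SAP 1.1. This is a reason for a light remedy, not for leaving the phrase as it is.

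**Conclusion.** The point holds in two parts. Aim 1b is wider than its outcome and hypothesis, so H4 can speak only to PrEP knowledge; this rests on the text alone. The H4 comparison is valid but gives up precision by setting aside pre-visit knowledge that the trial already collects. For a continuous score the variance of the arm difference would be multiplied by about 0.91, 0.75 or 0.64 at r = 0.3, 0.5 or 0.6. Those values of r are assumed, and the actual gain depends on how closely the pre-visit items relate to the t1 items. It would be too strong to say that pre-visit knowledge has no use anywhere, since SAP 3.1 leaves room for it in the baseline comparisons. The change should be made, but no primary result depends on it.

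**What to change.** 1. **SAP 3.3.2, H4.** Regress the t1 PrEP knowledge score on arm and the participant's pre-visit knowledge measure. Use a linear model if the score is continuous. If it is dichotomised, use a logistic model and report the risk difference standardised over the covariate, so that the result remains a marginal contrast comparable with the unadjusted one. Keep the chi-square or Fisher test as supplementary.
2. **SAP 1.1, Aim 1b.** Restrict it to knowledge of PrEP. Alternatively, if items on other methods are asked at t1, add an outcome in 2.1.2.2 and a hypothesis in 2.2 for them.
3. **SAP 2.1.2.2.** State that PrEP knowledge is asked at t1, how the questions are scored, and which pre-visit items form the covariate.

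The cost is SAP wording and one regression. Narrowing the aim needs no new data. Missing pre-visit values can be handled under the multiple imputation already planned for baseline characteristics in SAP 4.2. The changes should be fixed before anyone sees results by arm, so that neither the aim nor the covariate appears to have been chosen afterwards.
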